7.2 Treatments to be administered

Throughout the study, CZP dosing is fixed dose based on weight and given Q2W, with the exception of the lowest weight group on the reduced CZP regimen who will receive the maintenance dose Q4W. The loading dose, maintenance dose, and range of exposures in each weight category for both the original and reduced CZP regimens are presented in [Table 7-1](#). Study participants start with 3 loading doses of CZP at Weeks 0, 2, and 4 followed by a maintenance dose for the duration of the study. After Week 4 (Visit 5), home-based CZP administration by the study participant or parent/caregiver will be permitted between scheduled study visits.

A study participant's dosing category will only be changed after the confirmation of a weight change by the Investigator **at a scheduled clinic visit**.

The study participant will receive the dose of the next weight category once their weight crosses the 40kg/88lb boundary or crosses the 20kg/44lb boundary at a scheduled clinic visit. The study participant will continue on the dose of the new weight category regardless of potential decrease of the weight below the boundary. In case of significant weight fluctuations the Investigator should contact the Medical Monitor to discuss and confirm potential change in dosing if medically advised or discontinuation of treatment (eg, if related to AE).

The injection should be administered at either the lateral abdominal wall or upper outer thigh. Treatment of the injection site with an anesthetic cream prior to dosing is permitted.

Table 7-1 Dosing administration of CZP^a

| Weight range | Loading dose – Weeks 0, 2, and 4 (mg/kg dose range) IMP Description | Maintenance – Week 6 and onwards (mg/kg dose range) IMP Description |
|------------------------------|---|---|
| Original CZP regimen | | |
| 10 to <20kg (22 to <44lb) | 100mg Q2W (5-10mg/kg) 1 x 0.5mL inj | 50mg Q2W (2.5-5mg/kg) 1 x 0.25 mL inj |
| 20 to <40kg (44 to <88lb) | 200mg Q2W (5-10mg/kg) 1 x 1mL inj | 100mg Q2W (2.5-5mg/kg) 1 x 0.5mL inj |
| ≥40kg (≥88lb) | 400mg Q2W (<10mg/kg) 2 x 1mL inj | 200mg Q2W (<5mg/kg) 1 x 1mL inj |
| Reduced CZP regimen | | |
| 10 to <20kg (22 to <44lb) | 50mg Q2W (2.5-5mg/kg) 1 x 0.25mL inj | 50mg Q4W (2.5-5mg/kg) 1 x 0.25mL inj |
| 20 to <40kg (44 to <88lb) | 100mg Q2W (2.5-5mg/kg) 1 x 0.5mL inj | 50mg Q2W (1.25-2.5mg/kg) 1 x 0.25mL inj |
| ≥40kg (≥88lb) | 200mg Q2W (<5mg/kg) 1 x 1mL inj | 100mg Q2W (<2.5mg/kg) 1 x 0.5mL inj |

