8.4 Visits 5 to 10 (Weeks 4, 8, 12, 16, 20, and 24)

- Vital signs (within approximately 15 minutes prior to dosing and [pulse and blood pressure only] approximately 30 minutes after dosing)
- Height (Week 24 only)
- Weight (measurement used to reassess CZP dose according to [Table 7-1](#))
- Tanner stages (except growth; Week 24 only)
- Physical examination
- TB questionnaire (study participant and parent/caregiver) (Weeks 12 and 24 only)
- Hematology/biochemistry/urinalysis
- Reproductive potential and birth control
- Pregnancy (urine) test for postmenarcheal females (Weeks 8, 16, and 24 only)
- CRP
- PRINTO/PRCSG standard joint examination
- Physician's Global Assessment of Disease Activity (VAS)
- CHAQ-parent reported
- Parent's Assessment of Arthritis Pain (VAS)
- Parent's Global Assessment of Overall Well-Being (VAS)
- Clinically Inactive Disease
- Clinical remission on medication (at Week 24 only)
- DMS
- JADAS
- FPS-R for study participants ages 5 to 11 years (Weeks 4, 12, 16, and 24 only)
- JIA Pain VAS (standard version, Weeks 4, 12, 16, and 24 only for study participants ages 12 to 17 years)
- Fatigue Assessment Scale (Weeks 4, 8, 16, and 24 only)
- Juvenile Arthritis School Attendance and Caregiver Work Productivity Survey
- Concomitant medications and procedures
- Adverse events
- IXRS contact (Assignment of all required study medication until next scheduled visit.)

- CZP plasma concentrations (predose at Weeks 4, 12, 16, and 24. Study participants will return to the clinic site for a **postdose CZP plasma sample** approximately **5 to 7 days following the Week 16 visit.**)
- Anti-CZP antibodies (predose at Weeks 4, 12, 16, and 24)
- Autoantibodies (ANA and anti-dsDNA antibodies) (Week 16 only)
- CZP administration (At Week 4, self/parent/caregiver-administration under the supervision of the site staff for training. After Week 4, administration of study medication either by site personnel [for those not performing home-based administration] or self/parent/caregiver-administration under supervision of site personnel to ensure proper injection technique.)

Between scheduled visits (Weeks 6, 10, 14, 18, 22, 26, 28, 30), CZP will be administered at home by the study participant or parent/caregiver or study participants may visit the site for CZP administration by staff personnel.

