9 ASSESSMENT OF PHARMACOKINETICS AND IMMUNOLOGICAL VARIABLES

Blood samples will be collected predose to determine plasma concentrations of CZP and anti-CZP antibodies at Baseline (Week 0), Weeks 4, 12, 16, 24, 32, 40, 48, and then every 24 weeks thereafter; the Early Discontinuation/End of Treatment Visit, and the Final Visit 12 weeks after the last dose of study medication. For study participants enrolled prior to Protocol Amendment 9, samples for CZP plasma concentration and anti-CZP antibodies will no longer be collected. In addition, blood samples will be collected 5 to 7 days after dosing at Baseline (ie, at Week 1, Visit 3) and Week 16 (ie, return of study participant to clinic site at Week 17) to determine postdose plasma concentration.

All of these blood draws (except for postdose samplings at Week 1 and after Week 16) will be performed prior to any study medication administration, where applicable, and all of them coincide with the blood collection times for the assessment of hematology and clinical chemistry parameters, so that no additional blood draws are required at these visits except at Week 1 (Visit 3) and the postdose sampling following Week 16 (Visit 8). Time and date of each blood draw will be documented on the CRF.

Instructions on blood sample collection, processing, storage, and labeling/shipping will be provided in the laboratory manual for this study.

Blood samples to determine plasma concentrations of CZP and anti-CZP antibodies will be analyzed by a specialty laboratory. All study participants enrolled following Protocol Amendment 9 will have plasma concentrations of CZP and anti-CZP antibodies analyzed using an ECLIA method that meets current regulatory standards. In addition, PK and ADA samples (for which sufficient volume is available) collected in this study prior to Protocol Amendment 9 will be analyzed with the ECLIA method. The collective ECLIA-based PK data for this study will form the basis of any future CZP modeling and simulation work.

These plasma samples may be used additionally for analyses of CZP and its constituent moieties using alternative assay methods. The results of the analyses of CZP and its constituent moieties from alternative methods may be reported separately.

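### For the 10 to <20kg band on the reduced regimen, the Week 6 start of Q4W maintenance in Table 7-1 contradicts the predose and postdose labels given to the PK samples

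*Protocol*

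**What the plan says.** Section 7.2 sets dosing at Q2W, "with the exception of the lowest weight group on the reduced CZP regimen who will receive the maintenance dose Q4W". It states the loading scheme: "Study participants start with 3 loading doses of CZP at Weeks 0, 2, and 4 followed by a maintenance dose". In Table 7-1 one column header covers all six rows: "Maintenance – Week 6 and onwards (mg/kg dose range) IMP Description". The row for 10 to <20kg on the reduced regimen reads "50mg Q4W (2.5-5mg/kg) 1 x 0.25mL inj". No other start week is given for this group.

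Section 8.4 lists the home doses without a Q4W exception: "Between scheduled visits (Weeks 6, 10, 14, 18, 22, 26, 28, 30), CZP will be administered at home". Footnote y to Table 5-1 does mention Q4W home dosing between visits after Week 4 for the lowest weight group.

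On sampling, Section 9 says: "Blood samples will be collected predose to determine plasma concentrations of CZP and anti-CZP antibodies at Baseline (Week 0), Weeks 4, 12, 16, 24", continuing to Weeks 32, 40 and 48 and then every 24 weeks. Sections 8.4 and 9 describe a further postdose sample 5 to 7 days after the Week 16 dose. Table 5-1 and Sections 8.4 and 8.5 schedule CZP administration at these visits, again without a Q4W exception.

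Section 4.1.1 makes the Week 16 and Week 48 concentrations primary variables. Section 13.4 makes the ECLIA results the main PK evaluation and summarises them by dose regimen at each PK sampling visit.

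**The concern.** The visit and sampling schedule fits Q2W dosing, where each PK visit is also a dosing day. For the Q4W group the maintenance start in Table 7-1 and the sample labels in Sections 8.4 and 9 cannot both hold.

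On one reading, the Week 16 and Week 48 samples are taken halfway through a 28-day interval, and the Week 17 sample follows no dose since Week 14. On the other, they are end-of-interval samples and the Week 17 sample is a true postdose sample. A by-visit summary for the reduced regimen would combine these values with the Q2W predose values of the heavier bands, and the reader could not tell what the Q4W values represent.

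**Working it through.** **Inputs**
- Loading at Weeks 0, 2 and 4; maintenance from Week 6, Q4W (Section 7.2, Table 7-1). In this band loading and maintenance doses are both 50mg, so each dose counts as one unit.
- Clinic visits after Week 4: 8, 12, 16, 20, 24, then every 8 weeks from 32, window ±3 days (Table 5-1). PK visits after Week 4: 12, 16, 24, 32, 40, 48, then every 24 weeks (Section 9).
- Half-life about 14 days (Section 2). As a shorter alternative, Table 13-1 gives CL/F 0.253 and V/F 2.90 for ages 4 to 8. If the units are L/day and L (assumed; none are stated), half-life = 0.693 × 2.90 / 0.253 = 7.9 days.
- Absorption rate is not given: instantaneous in steps 3 and 4, 0.15 to 1.0 per day in step 5.

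**1. The plan's own list.** Q2W from Week 6 gives 6, 8, 10, ..., 30. Removing visit weeks 8, 12, 16, 20 and 24 leaves 6, 10, 14, 18, 22, 26, 28, 30, exactly the list in Section 8.4. So maintenance starts at Week 6, and the list assumes Q2W.

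**2. The Q4W calendar.**
- *Week 6 reading:* doses at 6, 10, 14, 18, ..., 46, 50. These weeks leave remainder 2 on division by 4, while every PK visit after Week 4 is a multiple of 4. There is no overlap, and the 14-day offset exceeds the ±3-day window. Weeks 16 and 48 each lie 14 days after one dose and 14 days before the next. The Week 17 sample is 19 to 21 days after the Week 14 dose.
- *Visit-week reading:* doses at 8, 12, 16, ..., 48. Every PK visit is a dosing day, but there is no Week 6 dose and no between-visit dose up to Week 24. Footnote y therefore fits the Week 6 reading up to that point.

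**3. Level at the primary visits.** Sum of 2^(−t/14) over earlier doses, t = days since each dose.
- Week 16 (day 112), Week 6 reading, t = 112, 98, 84, 70, 42, 14: 0.0039 + 0.0078 + 0.0156 + 0.0313 + 0.125 + 0.5 = 0.684.
- Week 16, visit-week reading, t = 112, 98, 84, 56, 28: 0.0039 + 0.0078 + 0.0156 + 0.0625 + 0.25 = 0.340. Ratio 0.684 / 0.340 = 2.0.
- Week 48, effectively steady state: 0.5 / (1 − 0.25) = 0.667 against 0.25 / (1 − 0.25) = 0.333. Ratio 2.0.

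**4. Week 17 sample** (5 and 7 days after Week 16; decay factors 2^(−5/14) = 0.781 and 2^(−7/14) = 0.707).
- Week 6 reading: 0.684 × 0.781 = 0.534 and 0.684 × 0.707 = 0.483, both below 0.684.
- Visit-week reading: (0.340 + 1) × 0.781 = 1.046 and 1.340 × 0.707 = 0.947, both above 0.340.

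**5. Sensitivity** (first-order absorption, 0.15 to 1.0 per day). The first row is the mid-interval level over the end-of-interval level, which at steady state is also the ratio between the two readings.

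| Quantity | Half-life 14 days | Half-life 7.9 days |
|---|---|---|
| Week 48, Week 6 reading over visit-week reading | 1.70 to 2.00 | 2.48 to 3.39 |
| Week 17 / Week 16, Week 6 reading | 0.71 to 0.85 | 0.54 to 0.76 |
| Week 17 / Week 16, visit-week reading | 1.75 to 3.06 | 2.85 to 7.35 |

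The direction is the same in every scenario; the size depends on the assumed half-life and absorption rate.

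**The case against.** The strongest reply is that the Week 6 header was written for a table in which five of six rows are Q2W, and that Table 5-1 and Sections 8.4 and 8.5 plainly put dosing at visits. Section 9 also says draws precede dosing where applicable, which allows for visits without a dose. This stands against the inference that Q4W doses never fell on PK visits: no section lists Q4W dose dates, so the text shows a conflict and not what was done. It does not remove the conflict, because a visit without a dose still cannot yield a predose sample in the labelled sense, nor a postdose sample a week later.

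Other strong inferences also fail:
- *That sites dosed differently.* Nothing shows this; the IXRS allocates medication centrally (Section 7.10).
- *That a planned trough summary is wrong.* Section 13.4 tabulates by visit and names no trough.
- *That exposure in the smallest children cannot be interpreted.* No concentration table by weight band is planned, and exposure modelling rests on PopPK, which with actual dose and draw times is unaffected by visit labels.

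The reply is also right that sampling on the reduced regimen has ended, so clarifying the text changes no stored sample. Its remaining point, that time since dose belongs in the SAP, does not excuse a contradiction inside the protocol.

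**Conclusion.** The protocol contradicts itself on when the Q4W group is dosed relative to its PK visits, and the documents do not settle which schedule applied. The two readings give Week 16 and Week 48 values about 2-fold apart with a 14-day half-life, and more with a shorter one. They also put the Week 17 sample on opposite sides of the Week 16 sample. The figures assume one compartment, unit doses and the stated absorption assumptions.

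The reach is limited to descriptive by-visit ECLIA summaries of participants who started on the reduced regimen in the 10 to <20kg band. The planned minimum is 10; fewer will contribute where stored volume is insufficient or the child has crossed 20kg. Participants moved to Q4W under Amendment 4 have a dosing phase set by their switch date and are summarised with the original regimen (Section 13.2.1). Those enrolled after Amendment 9 start on Q2W and are not affected. Because a primary variable is involved and the remedy is cheap, it should be corrected.

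**What to change.** Reconcile Table 7-1, Table 5-1 and Sections 8.4, 8.5 and 9 for the Q4W group; which dosing weeks apply is for the sponsor to decide.

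In Section 13.4, classify Q4W participants' ECLIA samples by actual days since last dose, using recorded draw times and documented dose dates. Present their Week 16, Week 17 and Week 48 values separately from the Q2W values, labelled predose, mid-interval or postdose. Do not pool them by nominal visit. Do not keep only 28-day values either: on the Week 6 reading no on-schedule Week 16 or Week 48 sample is 28 days after a dose, so that rule would empty both summaries for this band.

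The cost is small cells for this band and some work to derive time since dose. Draw times are on the CRF (Section 9). Home-dose dates are documented by caregivers (Section 7.2), but the protocol does not expressly place them on the CRF, so they may have to be retrieved from site records.

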7.2.1 Procedure for dose change (Protocol Amendment 9)

Following Protocol Amendment 9, study participants will only be enrolled on the original CZP dose regimen. With Protocol Amendment 4, the maintenance dose in the study was reduced by 50% for all weight groups (not applicable for study participants enrolled on the reduced CZP dose regimen per Protocol Amendment 5). Participants on the reduced CZP dose regimen can remain on the reduced CZP dose or may be switched to the original CZP dose regimen at the discretion of the Investigator and in consultation with the medical monitor. Additional dose changes are not allowed. The procedure for dose change is as follows:

- The timepoint of the dose change is the next scheduled time of injection after the Informed Consent form related to the dose change was signed. In case the next scheduled injection was planned for home dosing, the study participant will be requested to return to the clinic for an Unscheduled Visit for signing the Informed Consent form related to the dose change, administration of CZP, and to dispense the new supplies. Unused IMP dispensed previously needs to be returned.
In case the study participant is not able to visit the site for that next scheduled injection, then the dose change must be performed at the next scheduled injection.

- Study participants will be monitored at least every 4 weeks over a period of 12 weeks after the dose change, either at the regularly scheduled visits or at additional Unscheduled Visits. The Unscheduled Visits will be scheduled to match with the dosing schedule, ie, the study medication will be administered at the day of the Unscheduled Visit. The Investigator should consult with the Medical Monitor in case of any questions related to the timing of the dose change or the Unscheduled Visits.
 - Study participants undergoing the dose change at an Unscheduled Visit between the regular visits will be required to return at the latest after 4 weeks for an Unscheduled Visit in case no regular visit is scheduled within 4 weeks. These study participants will be monitored at least every 4 weeks over a period of 12 weeks.
- At Unscheduled Visits when the dose change occurs and following the dose change, the following will be assessed: AEs, concomitant medications and procedures, vital signs, hematology/biochemistry, as well as CRP, PRINTO/PRCSG standard joint examination, Physician's Global Assessment of Disease Activity, CHAQ, and Parent's Global Assessment of Overall Well-Being to determine PedACR response rates. Assessments at regular visits will be done as scheduled, except for PK sampling (see below).

7.3 Packaging

Certolizumab pegol is packaged and labeled according to Good Manufacturing Practice (GMP) guidelines and applicable laws or regulations. They are suitably packaged in such a way as to protect the IMPs from deterioration during transport and storage.

7.4 Labeling

Clinical drug supplies will be labeled in accordance with the current International Council for Harmonisation (ICH) guidelines on Good Clinical Practice (GCP) and GMP and will include any locally required statements. If necessary, labels will be translated into the local language. Details on Labeling will be provided in the Pharmacy manual.

7.5 Handling and storage requirements

The Investigator (or designee) is responsible for the safe and proper storage of IMP at the site. All IMPs must be stored in a secured, limited access area between 2 and 8°C (35.6 and 46.4°F) and protected from light.

Appropriate storage conditions must be ensured either by controlled temperature or by completing a temperature log in accordance with local requirements, but at least once a day with minimum and maximum temperatures reached over the time interval. A temperature out-of-range can be noted during storage at a site or during shipment at any time during the study.

In case a temperature out-of-range is noted during storage at a site, it must be immediately communicated to the Clinical Program Manager (CPM) (or designee) via the monitor before further use of the IMP. Site personnel have to complete the temperature excursion form during storage and fax it together with the temperature log form to the monitor. The monitor immediately has to inform Clinical Trial Supplies (CTS) at UCB who will place the affected medication in quarantine during the evaluation of the temperature excursion.

In case a temperature out-of-range is noted during shipment to a site, it must be immediately put in quarantine by contacting the IXRS and informing the monitor during the evaluation of the temperature excursion. For the maximum of information the temperature monitoring device has to be sent back immediately to the distributor.

After the evaluation of the temperature excursion, CTS will provide the monitor and the IXRS with instructions regarding further use of the product at the site.

For IMP dispensed to the study participant/caregiver for injection at home, the Investigator (or designee) will instruct the study participant/caregiver to store the IMP following the instructions on the label.

7.6 Drug accountability

A drug accountability form will be used to record IMP dispensing and return information on a by-study participant basis and will serve as source documentation during the course of the study. Details of any IMP lost (due to breakage or wastage), not used, disposed of at the study site, or returned to the Sponsor or designee must also be recorded on the appropriate forms. All supplies and pharmacy documentation must be made available throughout the study for UCB (or designee) to review.

Periodically and at the end of the study, all unused and expired investigational product (PFSs and containers) will be collected and sent to the Sponsor (or designee) for destruction. All used PFSs will be disposed of by site staff in an acceptable disposal (sharps) container directly after the administration. For CZP administration at home, the study participant/caregiver will receive a disposal (sharps) container in order to return used PFSs to the site for disposal. All containers of the used PFSs must be kept until the accountability is checked by the monitor and can be destroyed afterwards.

The Investigator (or designee) is responsible for retaining all used, unused, and partially used containers of IMP until returned or destroyed.

The Investigator may assign some of the Investigator's duties for drug accountability at the study site to an appropriate pharmacist/designee.

The Investigator must ensure that the IMP is used only in accordance with the protocol.

7.7 Procedures for monitoring study participant compliance

At each visit after IMP is dispensed, study participants must return all used, unused, and partially used IMP containers together with the documentation on home dosing, if applicable. Drug accountability must be done in the study participant's presence in order to obtain explanations regarding discrepancies in compliance with the dosing regimen. Drug accountability must be recorded on the Drug Accountability form.

If a study participant is found to be persistently noncompliant (missing 2 or more consecutive scheduled CZP doses or missing 3 or more doses over a 12-month period), the Sponsor in conjunction with the Investigator will make a decision as to whether the study participant should be withdrawn from the study.

This rule does not apply when CZP is discontinued if the study participant is in CRM or if CZP is temporarily discontinued due to an AE. The study participant will continue with

scheduled study visits even if not dosed. In the case of temporary discontinuation due to an AE, the Sponsor in conjunction with the Investigator will make a decision as to whether the study participant should be withdrawn from the study.

7.8 Concomitant medication(s)/treatment(s)

The sections below describe the following categories of concomitant medications/treatments: concomitant medications that are permitted during the study, rescue medications that are allowed before Week 16, rescue medications that are allowed after Week 16 and may be used for the remainder of the study, and concomitant medications that are prohibited at any time during the study.

7.8.1 Permitted concomitant treatments (medications and therapies)

The following are permitted:

- MTX, if being used:
 - Must have been stable for at least 1 month before Screening (Visit 1) at ≥ 10 to ≤ 15 mg/m² per week.
 - During the study, an increase is allowed only after Week 16 and to a maximum dose of 15 mg/m² per week.
 - Prior to Week 16, route of administration must not change. After Week 16, the route of administration may be changed.
 - During the study, the MTX dose may be decreased, but not discontinued. Methotrexate may be discontinued only for documented reasons of intolerance or toxicity, or in study participants who achieve CRM (persistent CID over a period of 6 months, as defined in Section 11.10) and only after discontinuation of CZP.
 - Study participants who do not maintain persistent CID following achievement of CRM can reinitiate therapy with MTX.
- Scheduled and as needed (PRN) use of NSAIDs, cyclooxygenase-2 (COX-2) inhibitors, acetaminophen (paracetamol), and other analgesics are permitted.
- Folic acid or folinic acid.
- Topical anesthetic creams (eg, lidocaine/prilocaine creams, licensed NSAID creams).
- Corticosteroids:
 - At study entry, the dose should have been stable for at least 7 days prior to the Baseline joint examination at a maximum dose of 10 mg or 0.2 mg/kg prednisone (or equivalent) per day, whichever is the smaller dose.
 - During the study, the dose of oral corticosteroids may be decreased but not initiated or increased above 10 mg or 0.2 mg/kg prednisone (or equivalent) per day, whichever is the smaller dose. The dose must be stable in the 7 days prior to a joint examination.
 - Initiation of topical corticosteroids is allowed for treatment of uveitis if developed during the course of the study.

- Intra-articular (ia) corticosteroids may be administered no more frequently than every 4 months and no more than up to 3 times in 1 year and only into up to 2 joints at a single time point.
- Any joint injected with ia corticosteroids will be excluded from the efficacy analysis for a period of 3 months.
- Intravenous (iv) corticosteroid use is permitted only for stress dosing for the purposes of surgery.
- Oral/parenteral/implantable hormonal contraceptives (stable for at least 2 months prior to Screening [Visit 1] if initiated prior to entering the study).
- Non-live and therefore permitted vaccinations include: intramuscular polio, Hepatitis A, Hepatitis B, pneumococcal conjugate vaccine (PCV), pneumococcal polysaccharide vaccine (PPSV), diphtheria-tetanus-pertussis (DTaP/DTP), Hemophilus influenzae type b (Hib), injectable (but not nasal) influenza, meningococcus, and human papilloma virus. The effectiveness of vaccines administered while on CZP treatment is currently unknown. (Live or live attenuated vaccines are prohibited during the course of the study.)

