Any confirmed diagnosis or suspicion of a latent or active TB infection is a reportable event. Either type of infection must be reported as an adverse event of special interest (AESI) and must be captured on an AE report form, ticking the appropriate AESI and, if applicable, serious adverse event (SAE) field(s) on the form to clearly indicate the level of seriousness. A UCB TB follow-up form also must be completed. Confirmed active TB is an SAE and must be captured on an SAE report form and provided to the Sponsor in accordance with SAE reporting requirements. As with all SAEs, periodic follow-up reports should be completed as per protocol requirements until such time as the TB infection resolves.

3. Study participant is found to be persistently noncompliant (missing 2 or more consecutive scheduled CZP doses or missing 3 or more doses over a 12-month period), the Sponsor in conjunction with the Investigator will make a decision as to whether the study participant should be withdrawn from the study (see Section 7.7).

This rule does not apply when CZP is discontinued if the study participant is in CRM or if CZP is temporarily discontinued due to an AE. In the case of temporary discontinuation due to an AE, the Sponsor in conjunction with the Investigator will make a decision as to whether the study participant should be withdrawn from the study.
4. Study participant takes prohibited concomitant medications as defined in this protocol (see Section 7.8.3).

Study participants may be discontinued from study medication (but not necessarily from the study) if any of the following occurs, but may be restarted after consultation with the Medical Monitor:

1. Study participant develops an illness that would interfere with continued participation (eg, malignancies).
2. If there is a positive pregnancy test, study medication will be held. If there is confirmed pregnancy, study medication must be discontinued until end of the pregnancy. In case the study participant intends to breastfeed after a pregnancy study medication must be further discontinued until end of breastfeeding.

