10.1.7 Pregnancy

Should a study participant become pregnant after the first intake of IMP, UCB Patient Safety should be informed immediately. Study medication must be discontinued as soon as pregnancy is known (by positive pregnancy test). Study participants can remain in the study under observation and should attend to scheduled visits regularly as their condition allows.

The Investigator must inform the study participant of information currently known about potential risks and about available treatment alternatives.

In cases where the partner of a male study participant enrolled in a clinical trial becomes pregnant, UCB will ask the Investigator or designee to contact the study participant and his partner to request consent via the Partner Pregnancy Consent Form. If the partner agrees to provide additional information, the Pregnancy Report and Outcome Form will be forwarded to the study participant's partner (or parent/caregiver if study participant underaged) for completion.

The pregnancy will be documented on the Pregnancy Report and Outcome Form provided to the Investigator. The progression of the pregnancy and the eventual birth (if applicable) must be followed-up using the Pregnancy Report and Outcome form in which the Investigator has to report on the health of the mother and of the child. The health of the child must be followed for 30 days after birth for any significant medical issues.

In certain circumstances, UCB may request that follow-up is continued for a period longer than 30 days.

A pregnancy becomes a serious adverse event (SAE) in the following circumstances: miscarriage, abortion, or anomaly/birth defect of the child. A pregnancy is considered as an SAE in case of contraceptive failure (eg, pill taken everyday at approximately the same time each day without having been forgotten or with use of permanent contraceptive devices). Those serious events must be additionally reported using the Investigator SAE report form.

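### The closed list of reasons for stopping methotrexate (7.8.1) omits pregnancy and breastfeeding, although 10.1.7 and 6.5 stop certolizumab pegol then and let the participant stay in the study

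*Protocol*

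**What the plan says.** Protocol 7.8.1 sets the general rule for MTX: "During the study, the MTX dose may be decreased, but not discontinued". The exceptions follow: "Methotrexate may be discontinued only for documented reasons of intolerance or toxicity, or in study participants who achieve CRM". For clinical remission on medication (CRM), 7.8.1 adds that CZP must already have been discontinued. One bullet deals with restarting: "Study participants who do not maintain persistent CID following achievement of CRM can reinitiate therapy with MTX".

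Pregnancy on study is handled in two other places. Section 10.1.7 requires study medication to stop at a positive test and continues: "Study participants can remain in the study under observation and should attend to scheduled visits regularly as their condition allows". Section 6.5 has the same stop: "If there is confirmed pregnancy, study medication must be discontinued until end of the pregnancy". It then extends it: "In case the study participant intends to breastfeed after a pregnancy study medication must be further discontinued until end of breastfeeding". In 6.5 these sentences sit under an introduction saying that the participant need not leave the study and that study medication may be restarted after consulting the Medical Monitor.

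The Summary (Section 1) identifies CZP as the investigational product. MTX is handled throughout as a permitted concomitant treatment.

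**The concern.** The protocol foresees pregnancy and breastfeeding and gives CZP a full path through them: stop, stay off, possibly restart. It gives MTX no such path. MTX is instead governed by a list closed by the word *only*, and that list was not written with pregnancy in mind. An investigator who follows 7.8.1 to the letter would keep a pregnant or breastfeeding participant on MTX, possibly at a lower dose, after CZP has been stopped.

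What is at stake is the safety of a participant and her child, and clear instructions to sites. The clinical weight rests on the risk of MTX to the fetus. That is general medical knowledge and is not stated in the protocol. The mismatch between the sections is visible without it.

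**Working it through.** No figure in the plan bears on this point, so there is nothing to recompute. The check is a comparison of the sections.

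**1. Which drug each rule covers**

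| Section | Drug | In pregnancy | In breastfeeding | Stays in study? |
|---|---|---|---|---|
| 10.1.7 | Study medication (CZP) | Stop at positive test | Not mentioned | Yes, with scheduled visits |
| 6.5 | Study medication (CZP) | Hold at positive test, stop once confirmed | Stop continues | Yes, not necessarily withdrawn |
| 7.8.1 | MTX | Not listed as a reason to stop | Not listed as a reason to stop | Not applicable |

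Section 7.8.1 lists 3 reasons for stopping MTX: intolerance, toxicity, and CRM after CZP has been discontinued. None of the 3 names pregnancy or breastfeeding. Of the 2 sections that stop CZP in pregnancy, neither names MTX.

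**2. Whether stopping CZP opens the CRM exception.** It does not. That exception needs both conditions: CRM, which 11.10 defines as at least 6 continuous months of clinically inactive disease (CID), and prior discontinuation of CZP. Pregnancy supplies only the second.

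**3. Whether another section supplies the exception**

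- 7.2 and 11.10 let the Investigator taper and stop MTX after CZP is fully stopped, but within the paragraph on participants who have reached CRM.
- 6.4 and 17.10 stop concomitant drugs that are not medically necessary, but only for potential drug-induced liver injury.
- Exclusion criteria 16 and 17 in 6.2 cover entry and contraception, not the management of a pregnancy that occurs on study.
- 12.1 and 14.3 allow departures in medical emergencies or to remove an immediate hazard. These are exceptions to the protocol, not instructions in it.
- 6.5 allows withdrawal for safety. That ends the participation that 10.1.7 means to preserve.

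**4. Whether the case can arise.** It can. Participants enter at ages up to 17 (6.1), postmenarcheal participants are tested for pregnancy during the study (10.7.7), and MTX at 10 to 15 mg/m² per week is permitted background treatment (6.1, 7.8.1). Treatment is open-ended: 5.1.1 puts the first participant's first visit in 1Q 2012 and the planned last participant's first visit in 3Q 2021, about nine and a half years later. Early participants can therefore reach adulthood on study.

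**5. Restart.** The MTX restart bullet in 7.8.1 is permissive and does not contain *only*. Section 7.8.2 counts starting MTX as rescue only in those not using it at entry, and 7.8.3 exempts MTX from the prohibited DMARDs. Restart after pregnancy is therefore unaddressed for MTX but not barred.

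**The case against.** The strongest reply is that no competent investigator would read 7.8.1 as an order to continue MTX in pregnancy, and that the rest of the protocol leaves enough room. Toxicity is not defined in 7.8.1 and is not expressly limited to harm that has already occurred, so a documented toxicity reason in pregnancy is arguable. The MTX dose may be lowered with no stated floor. Section 10.1.7 brings in the sponsor's safety group at once and adds: "The Investigator must inform the study participant of information currently known about potential risks and about available treatment alternatives". No penalty is attached to stopping MTX: it is neither rescue under 7.8.2 nor a trigger for withdrawal under 7.8.3. The consent form may also carry advice on MTX and pregnancy.

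Much of this stands, and it limits the practical harm. It does not remove the gap. Lowering a dose is not stopping it, informing a participant does not authorise a change, and a rule closed by *only* should not depend on a generous reading of one of its terms.

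Two stronger readings are tempting and go too far. A reader might infer that stopping MTX in pregnancy is certainly a protocol violation. The undefined term toxicity, and the emergency and hazard clauses, make that uncertain. A reader might also infer that MTX may be restarted only after loss of CID following CRM, so that a pregnancy rules it out for good. The restart bullet does not say that, and neither 7.8.2 nor 7.8.3 bars a restart in someone who was on MTX at entry.

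**Conclusion.** The point holds as a narrow participant-safety correction. The stated rule in 7.8.1, taken with 10.1.7 and 6.5, gives no planned route for stopping background MTX in a pregnant or breastfeeding participant who stays in the study. Nothing suggests that the sponsor intends MTX to continue; this reads as an exception left off a list.

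The event should be infrequent, since entry requires negative pregnancy tests and agreement to contraception. Its frequency cannot be estimated, because the protocol does not give the number of postmenarcheal participants on MTX. Participants on CZP monotherapy are unaffected while off MTX. No pharmacokinetic, safety or efficacy endpoint, sample size or error rate changes.

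The conclusion assumes that study medication means CZP alone, as the Summary indicates. Its clinical importance assumes the generally accepted fetal risk of MTX. The correction should be made, because it is specific and costs almost nothing.

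**What to change.** In 7.8.1, add a positive pregnancy test, pregnancy and breastfeeding to the permitted reasons for stopping MTX, and state that the CRM condition does not apply to them. In 10.1.7 and 6.5, state that concomitant MTX is stopped together with CZP at a positive pregnancy test and stays off through pregnancy and any breastfeeding. A sentence in 7.8.1 allowing MTX to be restarted afterwards would be a useful clarification but is optional.

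The cost is two or three sentences in an amendment and a notice to sites. No new data collection is needed and no analysis changes.
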